## 8.4 Baseline Study Questionnaire

The **Baseline Study Questionnaire** will collect: patient-reported ECOG performance status, SF-12 HR-QOL (the Optum SF-12 Health Survey uses 12 questions to measure functional health and well-being from the patient's point of view), information about the index VTE, cancer type/status, co-morbidities, influence of insurance coverage on decision to be participate, and demographics.

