**It is the enrolling site staff's responsibility to administer the Baseline Study Questionnaire to the participant.**

**Timing:** The Baseline Study Questionnaire must be administered after the participant has signed informed consent but before protocol treatment begins.

**NOTE:** The Baseline Study Questionnaire can be administered before or after the participant has been enrolled/ randomized as long as it is administered after the

participant has signed informed consent and before protocol treatment begins. It is operationally easiest to administer the Baseline Study Questionnaire immediately after the participant signs informed consent.

To administer the questionnaire:

- Print the questionnaire directly from Appendix: Baseline Study Questionnaire – for administration via paper
- Have the participant fill out the paper questionnaire
- Enter the participant's responses into REDCap (<https://redcap.partners.org>)
- Keep the original questionnaire in the participant's study file at your site

It is acceptable for a surrogate to complete the questionnaire on behalf of the patient. The surrogate can be a friend, family member, caregiver, or other appropriate person. The surrogate is NOT a research participant and should complete the questionnaire *on behalf of the patient*. No information about the surrogate will be collected.

If for any reason, the enrolling site staff is unable to administer the Baseline Study Questionnaire, they must notify the Central Study Coordinator immediately so that the Central Study Coordinator may attempt to administer the Baseline Study Questionnaire via phone, secure weblink, or postal mail. The Central Study Coordinator can be reached at: [contact] and/or CANVAS\[contact].

See 9.2 Data Submission using REDCap for instructions on how to enter and submit the data via REDCap.

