- i) *Health Related Quality of Life (SF-12) at 3 and 6 months*

For SF-12, the primary analysis variable is the difference in the SF-12 mean change score from baseline. We will consider 2-point differences as clinically meaningful. We will use multiple imputations to handle missing observations. First, we will create 10 complete datasets, imputing missing values using chained equations, where we include measurements at baseline, 3 months, and 6 months. Second, we will estimate mean changes and the standard errors for each of the 10 complete sets. We will then use Rubin's method to derive an estimate for the difference in the mean change score

between two groups. Using the resulting estimate and the standard error, we will perform a Z-test to evaluate equality of SF-12 scores between groups.

*ii) Anti-Clot Treatment Scale (ACTS) score at 3 and 6 months*

For ACTS score, the primary analysis variables are the ACTS Burdens total score and the ACTS Benefits total score at month 6. We will consider 2-point differences as clinically meaningful. To minimize potential bias due to missing observations, we will allow and include surrogate estimates for all 3 patient-reported outcome assessments. Next, we will use multiple imputation to handle missing observations. First, we will create 10 complete datasets, imputing missing values using chained equations, where we include measurements at baseline, 3 months, and 6 months. Second, we will estimate mean changes and the standard errors for each of the 10 complete sets. Lastly, we will integrate the results using Rubin's method.

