### **3.7. Other/Persistence with treatment endpoints**

- Performance status  
We will use the two-sample Wilcoxon test to evaluate between-group differences in ECOG PS.
- Cumulative rates of remaining on any anti-coagulation therapy at 3 and 6 months
- Cumulative rates of remaining on the assigned (and/or selected in the case of the preference cohort) anti-coagulation therapy at 3 and 6 months.
- 

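### SF-12 is compared as an unadjusted change from baseline, which gives up part of the precision available from the baseline score the trial already collects

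*Combined protocol and SAP*

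**What the plan says.** For SF-12 the SAP (3.6.2, item 4) i)) and the protocol (13.3.5, item 4a) use the same wording: "For SF-12, the primary analysis variable is the difference in the SF-12 mean change score from baseline". Ten datasets are completed by "imputing missing values using chained equations, where we include measurements at baseline, 3 months, and 6 months". The change is estimated in each and the results are pooled by Rubin's method. Then "we will perform a Z-test to evaluate equality of SF-12 scores between groups". The yardstick is also given: "We will consider 2-point differences as clinically meaningful". Neither section puts a covariate into the comparison.

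A baseline value is available. Protocol 8.4 lists "patient-reported ECOG performance status, SF-12 HR-QOL" among the baseline questionnaire items, and 8.6 repeats the SF-12 at 3 and 6 months.

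No other section supplies the adjustment:

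- The adjusted analysis in SAP 3.5.2.3 item 5 (protocol 13.3.3 item 5) is a logit-link mixed model under the VTE endpoint. SAP 3.6.2 carries it over to bleeding only.
- Its covariates are drawn from the SAP 3.4 list, which has a self-described global health item but no SF-12 score.
- Protocol 13.7 adds complete-case and multiple-imputation analyses, but no adjustment.

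**The concern.** Subtracting the baseline assumes that a patient who starts one point higher is expected to finish one point higher. With imperfect correlation and similar spread at both times, the expected gap at follow-up is smaller, so subtraction adds noise. A regression on baseline estimates the slope instead. In a large randomized comparison it cannot be less precise, and the two are equal only when the slope is 1.

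At stake is the width of the interval behind Hypothesis A (SAP 2.1), which says the arms have similar health-related quality of life. A similarity claim is only as good as its interval is narrow relative to 2 points. A non-significant test with a wide interval says little. The plan states no power for SF-12, since its power statement refers to recurrent VTE, so precision that costs nothing is worth taking.

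**Working it through.** **Inputs from the documents.** Threshold 2 points (SAP 3.6.2). Two-sided 5% level for this endpoint (SAP 3.1). 671 randomized, 1:1 (SAP 2.4 and 2.5), so about 335 per arm before any exclusion or non-response.

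**Inputs not in the documents, therefore assumed.** Correlation rho between baseline and follow-up SF-12: 0.4 to 0.7. Share f of follow-up scores observed: 1, 0.8 or 0.6. SD of 10 for one illustration. The plan gives no SF-12 precision or power figure to reproduce.

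**Step 1: complete data, equal SDs at both times.** Per patient:

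- Change score: variance 2·SD²·(1 − rho)
- Baseline-adjusted: variance SD²·(1 − rho²)
- Ratio, adjusted to change score: (1 + rho)/2

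At rho = 0.5 these are 1.00·SD² and 0.75·SD², ratio 0.75. Simulation with 335 per arm gave ratios of 0.66, 0.75 and 0.86 at rho 0.3, 0.5 and 0.7, against 0.65, 0.75 and 0.85 by formula. Both estimators were unbiased. Below rho = 0.5 the change score is noisier than ignoring baseline altogether (1.2·SD² against 1.0·SD² at rho = 0.4).

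**Step 2: allow for the planned imputation.** The imputation model already uses baseline, so the complete-data ratio overstates the loss when scores are missing. Suppose a share f is observed at random and the rest are imputed within arm from baseline. The variance of an arm mean (times n/SD²) is then:

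- Baseline-adjusted: (1 − rho²)/f
- Change score: (1 − rho²)/f + (1 − rho)²

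The ratio is (1 + rho)/[(1 + rho) + f(1 − rho)], and the equivalent extra sample is f(1 − rho)/(1 + rho). At f = 1 this returns Step 1. At rho = 0.5 and f = 0.8 the ratio is 1.5/1.9 = 0.79, and the extra sample is 0.4/1.5 = 27%.

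Gain as equivalent extra patients (fall in standard error in brackets):

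| rho | f = 1 | f = 0.8 | f = 0.6 |
|---|---|---|---|
| 0.4 | 43% (16%) | 34% (14%) | 26% (11%) |
| 0.5 | 33% (13%) | 27% (11%) | 20% (9%) |
| 0.6 | 25% (11%) | 20% (9%) | 15% (7%) |
| 0.7 | 18% (8%) | 14% (6%) | 11% (5%) |

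Using 3-month scores to impute month 6 would move the f < 1 figures part of the way back towards f = 1.

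**Step 3: illustration in points.** Take SD 10, 335 per arm and complete data. The 95% half-width for the change score is 1.96 × 10 × √(2(1 − rho)) × √(2/335). This gives 1.51 at rho 0.5 and 1.17 at rho 0.7. Replacing 2(1 − rho) by 1 − rho² gives 1.31 and 1.08. Power to detect 2 points rises from 0.735 to 0.85 at rho 0.5, and from 0.92 to 0.95 at rho 0.7. These are best cases, because they assume no missing scores.

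**The case against.** The planned estimator is conventional and valid, the endpoint is secondary, and no power is claimed for it. Neither the VTE analysis nor the type I error rate is touched. All of that stands. It limits how much the point matters but gives no reason to prefer the less precise estimator.

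It is also true that the baseline is not thrown away. It enters the change score with coefficient 1, and it enters the imputation model. Missing questionnaires are foreseeable: protocol 7.0 does not count them as violations, and 8.6 marks them missing after failed contacts. The complete-data figures are therefore upper figures.

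Four stronger readings are tempting, and the documents do not support them:

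- *Chance baseline imbalance is likely to distort the result.* Randomization has no stratification factors, but nothing suggests SF-12 would have been one. With 335 per arm the chance difference in baseline means has a standard error of √(2/335) = 0.077 SD, so it lies within about 0.15 SD in 95% of trials. At SD 10 and rho 0.5, a one-standard-error imbalance shifts the change-score contrast by 0.5 × 0.77, about 0.4 points. That is small against 2 points.
- *The change score is biased.* Over repeated randomizations it is not. The shift above is conditional on the imbalance that happens to occur.
- *Adjustment leaves the estimand untouched.* That is safe only where the groups are purely randomized. SAP 3.2 makes the primary population a modified ITT set restricted to patients who received their assigned strategy, and the preference cohort is not randomized. If baseline means differ there, the two contrasts can differ in expectation.
- *The performance-status analysis has the same fault.* SAP 3.7 says only "We will use the two-sample Wilcoxon test to evaluate between-group differences in ECOG PS". It does not say whether follow-up status or change is tested, so a loss is not established. A proportional-odds alternative would add an assumption the Wilcoxon test does not need.

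**Conclusion.** The point holds as a precision issue for SF-12 alone. The plan specifies an unadjusted change score, no other section adds adjustment, and the baseline score is collected. With equal SDs the direction of the loss is certain for any rho below 1. Its size is not fixed by the documents: over rho 0.4 to 0.7 and f 0.6 to 1, adjustment is worth between 11% and 43% more patients, or a standard error about 5% to 16% smaller. This rests on equal SDs at baseline and follow-up, scores missing at random, and imputation from baseline within arm. A reader should not infer that the planned SF-12 comparison is invalid, or that the VTE conclusions are affected.

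**What to change.** In SAP 3.6.2 item 4) i) and protocol 13.3.5 item 4a, replace the change-score comparison as follows. In each of the 10 imputed datasets, regress the 3-month and the 6-month SF-12 score on arm and baseline SF-12 (ANCOVA). Pool the arm coefficient by Rubin's method, and report the adjusted difference with its 95% CI against the 2-point threshold. Keep the unadjusted change score as a sensitivity analysis. State that in the modified ITT population and the preference cohort the two contrasts may differ if baseline means differ.

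The same edit should say how baselines completed after allocation was known are handled. The trial is unblinded, and the protocol's baseline questionnaire instructions allow this: "The Baseline Study Questionnaire can be administered before or after the participant has been enrolled/ randomized". This affects the change score as much as the regression.

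The cost is SAP and protocol wording and one regression per imputed dataset, with no new data. The change should be dated before SF-12 results by arm are examined. If they have already been seen, the adjusted analysis should be labelled as added afterwards.

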## **2. Study overview**

### **2.1. Objectives**

The primary objective of the study is to compare the effectiveness of anticoagulation with a DOAC (intervention) with LMWH/warfarin (comparator) for preventing VTE recurrence in patients with cancer. The hypothesis is that the benefit of secondary prophylactic anticoagulation with a DOAC is not worse than the benefit from treatment with LMWH/warfarin based on cumulative VTE recurrence reported by patients or their clinicians at 6 months.

The secondary objectives are:

- 1) To compare the harms of DOAC vs. LMWH/warfarin therapy for cancer patients with VTE based on the cumulative rate of major bleeding at 6 months.
- Hypothesis: The harms from DOAC therapy are not worse than the harms from LMWH/warfarin therapy based on the cumulative rates of major bleeding reported by patients or clinicians at 6 months.
- 2) To compare the impact of DOAC vs. LMWH/warfarin therapy on the experience and burden of anticoagulation therapy for cancer patients with VTE.
  - Hypothesis A: DOAC and LMWH/warfarin therapy are associated with similar overall HRQOL (health-related quality of life) at 3 and 6 months.
  - Hypothesis B: DOAC therapy is superior to LMWH/warfarin based on the Anti-Clot Therapy Scale at 3 and 6 months.
- 3) To compare the impact of DOAC vs. LMWH/warfarin therapy on mortality in cancer patients with VTE
  - Hypothesis: The risks of all-cause and cause-specific mortality for cancer patients treated with DOAC therapy are not worse than the risks for those treated with LMWH/warfarin based on survival at 6 months.

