## 3. Analysis methods and presentation

### 3.1. General principles

Analysis will be performed on the preference cohort and the randomized cohort separately. Where appropriate, variables will be summarized descriptively (frequency counts and percents for categorical variables, and counts, means, standard deviations (SD), medians, minimums, maximums, etc., for continuous variables) for two treatment groups – DOACs and Control. The primary analysis cohort is the randomized cohort. The secondary analysis cohort is the preference cohort. Using meta-analysis technique, the results from two cohorts will be combined.

We will construct 90% two-sided confidence intervals (CI) for the between-group comparisons for the analyses of VTE, bleeding, and mortality. A 90% two-sided CI corresponds to conducting a statistical test at a one-sided 5% significance level. For the other analyses, all confidence intervals, statistical tests, and resulting p-values will be reported as two-sided and assessed at the 5% significance level. If the computed lower confidence bound for proportion variables is less than -1, then the lower bound is defined as -1. If the computed upper confidence bound for proportion variables is greater than 1, then the upper bound is defined as 1.

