## 3.6. Secondary endpoint evaluation

### 3.6.1. Secondary endpoints

- Cumulative incidence of major bleeding reported by either patients or clinicians at 6 months
- Cumulative incidence of all bleeding events and bleeding according to its severity in the following categories: 1) major bleeding, 2) clinically significant non-major and 3) nuisance
- Cumulative incidence of death at 6 months
- Overall HRQOL at 3 and 6 months
- Overall score on the Anti-Clot Therapy Scale at 3 and 6 months

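### SF-12 similarity rests only on an equality test, with no conclusion tied to the SAP's own 2 points; the ACTS analysis text does not match its endpoint and names no test

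*Combined protocol and SAP*

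**What the plan says.** **SF-12.** SAP 2.1, Hypothesis A (Hypothesis 3a in protocol 2.0), states: "DOAC and LMWH/warfarin therapy are associated with similar overall HRQOL (health-related quality of life) at 3 and 6 months". SAP 3.6.2, item 4(i), analyses the between-arm difference in mean change from baseline after multiple imputation, and says that "we will perform a Z-test to evaluate equality of SF-12 scores between groups". Protocol 13.3.5 has the same text. The item also states: "We will consider 2-point differences as clinically meaningful". SAP 3.1 limits 90% intervals: "We will construct 90% two-sided confidence intervals (CI) for the between-group comparisons for the analyses of VTE, bleeding, and mortality". For everything else, "all confidence intervals, statistical tests, and resulting p-values will be reported as two-sided and assessed at the 5% significance level".

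**ACTS.** SAP 2.1, Hypothesis B, states: "DOAC therapy is superior to LMWH/warfarin based on the Anti-Clot Therapy Scale at 3 and 6 months". The endpoint listed in SAP 3.6.1 is "Overall score on the Anti-Clot Therapy Scale at 3 and 6 months". SAP 3.6.2, item 4(ii), makes two totals primary, Burdens and Benefits, both at month 6. It then describes imputation using measurements at baseline and both follow-up visits, estimation of mean changes, and pooling by Rubin's method. The item ends there.

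**The concern.** An equality test looks for evidence of a difference. Failing to find one does not show similarity, because the result depends on how many patients respond as well as on the true effect. With few responders, a real 2-point difference would often be non-significant. With many, a difference that the SAP does not call meaningful could be significant. The plan has a threshold but does not connect it to what may be concluded. It also names neither the SF-12 score nor the visit that decides.

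For ACTS, the endpoint list, the named analysis variables and the analysis steps describe different quantities, and no comparison between arms is specified for a superiority hypothesis.

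Patient experience and burden form one of the four study objectives, so these statements will be read as findings.

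**Working it through.** **No stated figure to reproduce.** The documents give no SD, response rate, power or margin for SF-12 or ACTS.

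**Inputs from the documents.** The randomized cohort is 671 at 1:1 (SAP 2.5 and 2.2), so 671/2 = 335.5, taken as 335 per arm. This is an upper limit, since the modified ITT set leaves out patients who did not receive their assigned strategy (SAP 3.2). The clinically meaningful difference is 2 points (SAP 3.6.2). The test is two-sided at 5% (SAP 3.1).

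**Assumptions.** The SD of the SF-12 change score is 8, 10 or 12. The number of informative responders is 335 per arm, or 200 per arm as a lower case. One score at one visit is judged.

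**Step 1: standard error.** SE = SD × √(2/n).
- 335 per arm: 0.618, 0.773, 0.927.
- 200 per arm: 0.800, 1.000, 1.200.

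**Step 2: chance that a true 2-point difference is non-significant.** P = Φ(1.96 − 2/SE) − Φ(−1.96 − 2/SE). For SD 8 at 200 per arm, 2/SE = 2.5 and Φ(−0.54) = 0.29; the second term is negligible.

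| Per arm | SD 8 | SD 10 | SD 12 |
|---|---|---|---|
| 335 | 0.10 | 0.26 | 0.42 |
| 200 | 0.29 | 0.48 | 0.62 |

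**Step 3: smallest observed difference that is significant.** At 335 per arm, 1.96 × SE = 1.21, 1.51 and 1.82 points. All are below 2.

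**Step 4: the alternative rule.** Similarity is concluded only if the interval lies within −2 to +2. For true difference d, P = max(0, Φ((2−d)/SE − z) − Φ((−2−d)/SE + z)), with z = 1.645 for a 90% interval and 1.96 for a 95% interval.
- At d = 2, the 90% rule wrongly concludes similarity with probability at most 0.05 in all six cases.
- At d = 0, it concludes similarity as follows:

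| Interval, per arm | SD 8 | SD 10 | SD 12 |
|---|---|---|---|
| 90%, 335 | 0.89 | 0.65 | 0.39 |
| 90%, 200 | 0.61 | 0.28 | 0.02 |
| 95%, 335 | 0.80 | 0.47 | 0.16 |
| 95%, 200 | 0.41 | 0.03 | 0 |

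**Step 5: how the SAP treats its other outcomes.** VTE recurrence has a rule comparing the interval with 3% (SAP 3.5.2.1). Major bleeding has one with 2.5% (SAP 3.6.2, item 1). Mortality also has a not-worse hypothesis, but the SAP says that it is underpowered for a confirmatory analysis and will be reported as quantitative information (item 3). SF-12 has neither a rule nor such a statement.

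**Step 6: ACTS texts side by side.**
- Score: one overall score in SAP 3.6.1; separate Burdens and Benefits totals in SAP 3.6.2. Protocol 8.10 describes the 12-item and 3-item scales and defines no overall score.
- Variable: totals at month 6, then mean changes with baseline measurements. The baseline questionnaire content in protocol 8.4 lists SF-12 but not ACTS; protocol 8.6 lists ACTS at follow-up. The forms are not enclosed (protocol 17.0).
- Test: none named.

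**The case against.** The strongest reply on SF-12 is that the harm is conditional. A reader might infer that the plan will declare similarity whenever the Z-test is non-significant. No passage says so. The analysis yields an estimate and a standard error, SAP 3.1 provides for two-sided reporting at 5%, and a reader could compare the interval with 2 points unaided. That stands as a limit on the claim. It does not close the gap, because the hypothesis asserts similarity and the only inference planned for it is the equality test. It is also fair that a clinically meaningful difference is not automatically an equivalence margin; the sponsor would have to adopt it as one.

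On ACTS, a reader might infer that the score and visit are wholly undetermined. They are not: SAP 3.6.2 names the two totals at month 6, and month 3 can be read as supportive. The protocol version names no month, but protocol section 13 presents itself as selected references from the SAP, so that silence is not a conflict. A reader might also infer that ACTS was not collected at baseline. The summary list suggests this, but the form is not available and SAP 3.6.2 speaks of three patient-reported assessments. This is a question for the sponsor.

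Finally, a reader might infer that treatment arm is left out of the imputation model. The text neither includes nor excludes it, so no bias can be claimed.

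**Conclusion.** The SF-12 point holds. The planned test cannot support Hypothesis A, and the SAP's 2 points govern no conclusion. Reading non-significance as similarity would accept a true 2-point difference with probability 0.10 to 0.42 at 335 per arm, or 0.29 to 0.62 at 200. The interval rule holds this at 0.05 or less. In the other direction, at 335 per arm, observed differences of about 1.2 to 1.8 points would already be significant. These sizes depend on the assumed SDs and response; the logical gap does not.

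The ACTS point holds in a narrower form: one overall score against two totals, changes from a baseline that the protocol does not list for ACTS, and no named test for superiority.

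Both concern secondary endpoints. Nothing here touches the primary VTE conclusion.

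**What to change.** **SF-12.** Do not base Hypothesis A on the equality test. Report the confidence interval for the difference in mean change, conclude similarity only if it lies within −2 to +2, and otherwise call the result inconclusive. The sponsor should confirm 2 points as the margin and name the SF-12 score and the deciding visit. The interval can be 90%, written as a named exception to SAP 3.1, which itself notes that "A 90% two-sided CI corresponds to conducting a statistical test at a one-sided 5% significance level"; or the default 95% can be kept. If no margin is acceptable, restate Hypothesis A as estimation only, as the SAP does for mortality, and draw no similarity conclusion. Align protocol 13.3.5.

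**ACTS.** Confirm whether it was collected at baseline. If not, remove the references to baseline and to changes, and compare the Burdens and Benefits totals between arms at month 6 as primary, with month 3 supportive. Name the test, state how the two totals together decide Hypothesis B, and align the endpoint in SAP 3.6.1.

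**Imputation.** At most, confirm that treatment arm is in the model.

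**Cost.** Wording and analysis code; no new data. The real price is that the SF-12 result may be inconclusive even if the arms are identical: at SD 10 the 90% rule succeeds with probability 0.65 at 335 per arm and 0.28 at 200. The 95% interval avoids the exception to SAP 3.1 but lowers these to 0.47 and 0.03. Requiring similarity at both visits could not raise any of these figures.

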### **2.2. Study Design**

The study design is a randomized effectiveness study to evaluate the effectiveness of DOAC therapy compared to usual care with LMWH/warfarin. Eligible patients who accept randomization will be enrolled in the study (the randomized cohort), and they will be randomly assigned either the DOAC therapy group or the usual care group at a 1:1 ratio. Those patients who decline randomization but choose treatment on one of the two study arms will be invited to the study (the preference cohort). The rationale of employing the hybrid study design with the two cohorts is that both cohorts have their own strengths, and they complement each other. Specifically, the randomized controlled design is the most rigorous study design for comparing treatment alternatives. However, it may not capture the effectiveness under the real-world setting because the analysis population is limited to only those patients who accept randomization. On the other hand, the non-randomized study (i.e., the preference cohort) assesses the effectiveness that more likely occurs under real-world circumstances, while the internal validity (i.e., the comparability between the two treatment groups) has to rely on unverifiable assumptions. This hybrid study design will maximize the totality of evidence of comparative effectiveness between the DOAC and usual care. All statistical analyses (details below) will be performed with the randomized cohort and the preference cohort separately, and they will be combined using a

meta-analytic methodology (details below). The results from the randomized cohort will be considered the primary results.

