## 2.5. Sample size justification

The protocol (Section 13.2.4) stated that:

- As of April 28, 2020, the study has enrolled a total of 808 patients. Of the 808, 668 were enrolled in the randomized cohort. When we discontinue the patient enrollment now, the total sample size is expected to be around 810 depending on the exact date of formal closure. With this sample size, the power of noninferiority test already reaches 90% (See Table). For superiority, it is slightly below the 80% target power at 75%. The expected length of confidence interval (CI) for the difference in event rate is now 6.1% with 808 patients, and it would have been 5.8% with the planned total sample size (N=890). This suggests that the gain in the precision may be marginal. Given the challenges to continued accrual in the setting of the COVID-19 pandemic and the recently reported results of the Caravaggio study we propose revision as follows.
- 

Table: Power calculation for the primary analysis

Date	N (Randomized Cohort)	N (total)	Length of CI for difference	Power	
				Noninferiority	Superiority
Revised Statistical Analysis Plan	668	808	6.1%	0.900	0.756
Originally Planned Goal	750	890	5.8%	0.927	0.797

Note that the termination of the new enrollment to the CANVAS trial therefore was approved by the AFT DSMB in April 2020 before reaching the original proposed 890 patient accrual mark. Upon formal study closure at all sites, the final total sample size was 811 (140 in the preference cohort, 671 in the randomized cohort).

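### Two separate, minor defects in the SF-12 analysis: a normal reference for an estimate pooled over 10 imputations (true level about 0.051 to 0.058), and too few imputations to hold a borderline p-value steady between random seeds.

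*Combined protocol and SAP*

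**What the plan says.** SAP section 3.6.2, item 4) i), sets out the SF-12 analysis in three steps, and protocol section 13.3.5, item 4) a, repeats it:

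- Imputation: "First, we will create 10 complete datasets, imputing missing values using chained equations".
- Pooling: "We will then use Rubin's method to derive an estimate for the difference in the mean change score".
- Testing, from the pooled estimate and its standard error: "we will perform a Z-test to evaluate equality of SF-12 scores between groups".

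SAP section 3.1 fixes the level. SF-12 is not among the VTE, bleeding and mortality analyses that get 90% intervals, so it falls under the rule that "all confidence intervals, statistical tests, and resulting p-values will be reported as two-sided and assessed at the 5% significance level". The same SF-12 item adds a yardstick: "We will consider 2-point differences as clinically meaningful".

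Neither document gives degrees of freedom, a random seed, a limit on Monte Carlo error, a rule for raising the number of imputations, or an expected SF-12 missing rate. No confidence interval formula is written for SF-12. The ACTS item next to it also uses 10 imputed datasets and Rubin's method but names no test. Protocol section 13.7 plans complete case analyses alongside multiple imputation.

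**The concern.** Rubin's method has two parts: a pooled variance that includes the between-imputation component, and a t reference that allows for that component being estimated from only m datasets. The plan adopts the first part and replaces the second by a normal distribution. With m = 10 this errs on the anti-conservative side, so the test rejects slightly more often than 5%.

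The second problem does not depend on the first. The pooled estimate is an average over 10 random completions of the data. A new seed gives a new average, and with m = 10 the difference is visible when the p-value lies near 0.05. With no seed fixed in advance, two analysts following the plan exactly could report results on opposite sides of the threshold.

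At stake is the reported test for the quality-of-life hypothesis, a secondary objective, in an unblinded trial. Some missing SF-12 data are foreseeable. Protocol section 8.6 marks a questionnaire as missing after repeated failed contacts, section 8.8 allows withdrawal from the questionnaires alone, and section 7.0 does not count a missing questionnaire as a violation.

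**Working it through.** **Inputs.** From the documents: m = 10, Rubin pooling, a normal reference and two-sided 5%. On size, "the final total sample size was 811 (140 in the preference cohort, 671 in the randomized cohort", with 1:1 allocation, which is about 335 per arm. This is an upper bound, because the modified ITT number is not given. Assumed, because the documents give neither: FMI from 0.2 to 0.5, and a standard deviation of SF-12 change from 8 to 12 points. The plan states no power, standard deviation or missing rate for SF-12, so it has no figure to reproduce.

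**Formulas.** Let B be the between-imputation variance, T the total variance and FMI = (1 + 1/m)B/T.

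- Rubin degrees of freedom: df = (m − 1)/FMI².
- Actual level of the Z-test: 2 × P(t_df > 1.96).
- Shortfall of a normal-based interval: 1 − 1.960/(t critical value).
- Between-seed SD of the pooled estimate: √(B/m), which is √(FMI/(m + 1)) in units of its standard error (SE).

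For example, at FMI 0.3 and m = 10: df = 9/0.09 = 100, and between-seed SD = √(0.3/11) = 0.165 SE.

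| FMI (assumed) | df, m = 10 | Correct critical value | Actual level of Z-test | Interval too narrow by | Seed SD, m = 10 | Seed SD, m = 50 |
|---|---|---|---|---|---|---|
| 0.2 | 225 | 1.971 | 0.0512 | 0.54% | 0.135 SE | 0.063 SE |
| 0.3 | 100 | 1.984 | 0.0528 | 1.2% | 0.165 SE | 0.077 SE |
| 0.4 | 56 | 2.003 | 0.0550 | 2.2% | 0.191 SE | 0.089 SE |
| 0.5 | 36 | 2.028 | 0.0578 | 3.4% | 0.213 SE | 0.099 SE |

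**Check of the level.** Simulation with 300,000 replicates gave Z-test levels of 0.052, 0.052, 0.055 and 0.058 down the table. The t reference gave 0.049 to 0.051. Barnard-Rubin degrees of freedom with 669 complete-data df change little: the largest shortfall becomes 3.7%.

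**Seed effect on a p-value.** Take FMI 0.3 and a result at z = 1.96.

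- m = 10: 1.96 ± 1.96 × 0.165 runs from 1.636 to 2.284, or p = 0.10 to 0.02.
- m = 50: 1.96 ± 1.96 × 0.077 runs from 1.81 to 2.11, or p = 0.07 to 0.035.

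These ranges count noise in the estimate only. Re-imputing a fixed dataset 100,000 times also lets the variance estimate vary. When the p-value with unlimited imputations is 0.05, the 95% range of p is then 0.017 to 0.127 with m = 10, 0.032 to 0.077 with m = 50 and 0.036 to 0.068 with m = 100. If that p-value is 0.04, two seeds at m = 10 disagree on significance with probability 0.44 to 0.48 over FMI 0.2 to 0.5. If it is 0.03, the probability is 0.23 to 0.41.

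**Are the two effects linked?** At FMI 0.3 and m = 10, switching to the t reference changes the simulated range from 0.017–0.127 to 0.018–0.134. The t-test therefore does not cure the seed problem; a larger m does.

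**Seed effect in points.** With 335 per arm, and FMI here taken at its large-m value, SE = SD × √(2/335)/√(1 − FMI) and seed SD = SE × √(FMI/10).

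- FMI 0.3: SE is 0.739 (SD 8) to 1.108 (SD 12), and seed SD is 0.13 to 0.19 points.
- FMI 0.5: SE is 0.874 to 1.311, and seed SD is 0.20 to 0.29 points.

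All are well below 2 points.

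**The case against.** The best defence is that the error is tiny. Rubin's variance already carries the (1 + 1/m)B term, so the normal reference costs at most about 0.8 percentage points of level, and Z and t disagree on significance in no more than 0.7% of null trials even at FMI 0.5. The upper end of the FMI range may be pessimistic, because the plan allows surrogate completion, repeated contact attempts and a gift card for each completed follow-up questionnaire. The seed matters only near p = 0.05, and 50 imputations reduce the flipping without removing it. The hypothesis is that quality of life is similar, so slight over-rejection of equality works against the trial's own claim. All of this stands, and it keeps the point minor. It gives no reason to prefer the stated method.

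A reader might also infer four stronger things that the documents do not support:

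- That the normal reference causes the seed instability. It does not; the small m does.
- That the SF-12 conclusion rests on this one test. The Z-test is the only test named for SF-12, but protocol section 13.7 adds complete case analyses, which have no seed, and the 2-point yardstick also applies.
- That ACTS has the same testing error. Its item names no Z-test.
- That the plan prescribes intervals that are too narrow, or that heavy missingness is expected. No SF-12 interval formula or missing rate is written, so a normal-based interval is only implied by the Z-test.

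**Conclusion.** The point holds as two separate and minor defects in a secondary analysis. The normal reference makes a nominal 5% test run at about 0.051 to 0.058, and an implied interval would be about 0.5% to 3.4% too narrow. Separately, 10 imputations without a fixed seed leave between-seed noise of about 0.13 to 0.21 SE, enough to carry a result near p = 0.05 across the threshold but small in SF-12 points. Of the two, the seed noise has more practical weight.

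These sizes rest on an assumed FMI of 0.2 to 0.5. At lower FMI both effects shrink: at 0.1 the level is 0.0503 and the seed noise 0.095 SE. The figures in points also rest on the assumed standard deviation of 8 to 12 and on 335 per arm. A reader should not conclude that the quality-of-life comparison is seriously miscalibrated. The primary VTE conclusion is not touched.

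**What to change.** In SAP section 3.6.2, item 4) i), and protocol section 13.3.5, item 4) a, replace the Z-test by a t-test, with its matching interval, using Rubin or Barnard-Rubin degrees of freedom. In the same place, use at least 50 imputations, record the seed before the analysis is run and report the Monte Carlo error. With m = 50 the choice between Z and t hardly matters (level 0.0502 to 0.0514 over FMI 0.2 to 0.5), but the t reference is still the one that belongs to Rubin's method.

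For ACTS, in the SAP and in the protocol, make only the change to at least 50 imputations with a recorded seed.

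The cost is about one sentence in each item, trivial extra computing and slightly larger SF-12 p-values.
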